## Secondary outcomes

Name	Method and metric	Time points of data collection
Pressure ulcer category II, III, IV, Unstageable, DTI at heels or sacrum	
 
• Clinical assessment using the NPUAP PU classification system
 
• Proportions developed per 1000 bed days (incidence)
 
	D0 and once daily
Pressure ulcer category I (non-blanchable erythema) at heels and/or sacral area	
 
• Clinical assessment using the NPUAP PU classification system
 
• Proportions developed from baseline until end of study (cumulative incidence)
 
	D0 and once daily
Pressure ulcer category I (non-blanchable erythema) at heels and/or sacral area	
 
• Clinical assessment using the NPUAP PU classification system
 
• Proportions developed per 1000 bed days (incidence)
 
	D0 and once daily
Days free of sacral and/or heels pressure ulcers category I, II, III, IV, DTI	
 
• Clinical assessment using the NPUAP PU classification system
 
• Number
 
	D0 and once daily
Resources associated with heel and sacral PU prevention	
 
• Preventive dressings (n), time for dressing application (minutes; data source: estimation)
 
• Type of support surface (standard, special elastic foam, viscoelastic foam, low air loss overlay/mattress, alternating air mattress; data source: clinical records and direct observation)
 
• Type of turning (30° degrees left/right, supine, prone, other; data source: clinical records)
 
	D0 and once daily
Resources associated with heel and sacral PU treatment	
 
• Wound assessments (number and times; data source: clinical records and estimation)
 
• Wound infection diagnoses, e.g. swabs, biopsies (number, times; data source: clinical records and estimation)
 
• Therapeutic primary and secondary dressings (numbers, types), time for dressing application/changes (minutes; data source: clinical records and estimation)
 
• Debridement (numbers and types incl. material; data source: clinical records and estimation)
 
• Systemic antimicrobial treatment because of PU wound (number, types; data source: clinical records)
 
	D0 and once daily

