**Figure 3. Data collection and management**

## 5.2 Statistical methods

Depending on the level of measurement (nominal, ordinal, continuous) variables will be described using absolute and relative frequencies or arithmetic means, medians and spread parameters (minimum, maximum, interquartile ranges, standard deviations). Baseline demographic (age, gender, PU risk etc.) and clinical characteristics (e.g. medical diagnoses, duration of ventilation) of each group will be displayed in a table.

The primary end point PU incidence category II, III, IV, DTI at heels and/or sacrum will be compared using a Chi-squared test. This will be the main analysis of this primary outcome. A logistic regression will be applied to adjust for baseline covariates. An alpha level of 5% (two-sided) will be applied. Kaplan-Meier analyses and logrank test will be used to compare the times to development of a new PU between groups. Multiple Cox regression analysis will be performed to adjust for potential confounders. Data will be analysed as intention to treat.

Secondary outcomes will be analysed in a similar way. Depending on the level of measurement (nominal, ordinal, continuous) secondary outcomes will be described using absolute and relative frequencies or arithmetic means, medians and spread parameters (minimum, maximum, interquartile ranges, SDs). Chi-squared or t-tests will be applied to compare groups. In case of normality assumption being violated, the Mann-Whitney U test will be used instead of t-test.

For daily measurements, missing values will be imputed via LOCF method, and the results will be compared to those without imputation.

A cost effectiveness analysis (CEA) comparing both groups will be conducted. Quantities of used preventive dressings including labor costs for application in the intervention group and quantities of used PU treatment materials (e.g. dressings, time) will be documented. Current market prizes in Euro will be used to calculate the total costs per group. An incremental cost effectiveness ratio (ICER) will be calculated by dividing the mean differences in costs by the mean differences in effects. In order to make results comparable a similar approach like the work by Santamaria et al. 2013b will be used.

All analytic steps including the CEA will be repeated for the two subgroups heel PUs and sacral PUs.

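### The planned ICER has no stated measure of uncertainty although about 15 events are expected; separately, the listed costs leave out support surfaces that are recorded daily

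*Combined protocol and SAP*

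**What the plan says.** Cost-effectiveness is the last secondary objective in section 2.2. The method is one paragraph of section 5.2, which obtains the ICER by "dividing the mean differences in costs by the mean differences in effects". The effect measure is not named. No interval, bootstrap, net benefit or sensitivity analysis is mentioned, and there is no rule for an effect difference of zero or below. The paragraph ends by pointing to a published analysis: "In order to make results comparable a similar approach like the work by Santamaria et al. 2013b will be used". The section then extends the method by site: "All analytic steps including the CEA will be repeated for the two subgroups heel PUs and sacral PUs".

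The cost items are "Quantities of used preventive dressings including labor costs for application in the intervention group" together with quantities of pressure ulcer (PU) treatment materials. Market prices "will be used to calculate the total costs per group".

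Section 3.4 has a secondary outcome called "Resources associated with heel and sacral PU prevention", collected at D0 and once daily. Besides the preventive dressings and their application time, it covers the type of support surface and the type of turning. The table of other variables adds days on each support surface, and position type with hours in position. Section 3.3 puts both arms under the same hospital prevention standard apart from the dressings. Section 4.4 says that caregivers and study staff are not blinded.

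**The concern.** There are two separate gaps.

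The first is in the denominator. An ICER divides by an effect difference that will be estimated from few events. Reported as a point value, it does not tell the reader whether the data fit a cost per PU avoided several times higher or lower, or no benefit at all. A ratio also behaves badly near zero: it is undefined at zero and changes sign beyond it.

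The second is in the numerator. Support surface is collected as a prevention resource but is missing from the listed costs, so each group's total is incomplete as written. If staff who can see the dressings choose other support surfaces for those patients, the incremental cost is off as well.

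At stake is the answer to one secondary objective. The primary comparison does not depend on any of this.

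**Working it through.** **Inputs.** Section 3.6 gives a control incidence of 0.06, an intervention incidence of 0.01, 211 per arm, power 0.8 and two-sided alpha 0.05. The effect is taken as PUs avoided (the difference in cumulative incidence), because section 5.2 does not name one. The documents give no unit prices or cost variances, so no ICER can be computed. The cost difference is held fixed and only the denominator varies.

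**The plan's own figure.** With pooled variance and no continuity correction,
n = [1.96·√(2·0.035·0.965) + 0.842·√(0.06·0.94 + 0.01·0.99)]² / 0.05² = 211 per arm, with power 0.800. Section 3.6 reproduces.

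**Expected events.** 211·0.06 + 211·0.01 = 12.66 + 2.11, or about 15 in total.

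**Precision at the planning rates.** SE = √(p₁q₁/211 + p₂q₂/211) = 0.0177. The 95% interval is 0.050 ± 1.96·0.0177 = 0.0153 to 0.0847. With a fixed cost difference the ICER is proportional to 1/difference. It therefore runs from 0.050/0.0847 = 0.59 to 0.050/0.0153 = 3.3 times its point value. The ends differ by a factor of about 5.6 (5.55 before rounding). The exact binomial probability of an observed difference at or below zero is 0.2%.

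**Other settings.** These rates are assumptions, chosen to show the range. Probabilities are exact binomial.

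| Setting | Rates | n per arm | Difference, 95% interval | P(difference ≤ 0) |
|---|---|---|---|---|
| Planning | 0.06 vs 0.01 | 211 | 0.050 (0.0153 to 0.0847) | 0.2% |
| Weaker effect | 0.06 vs 0.03 | 211 | 0.030 (-0.0095 to 0.0695) | 8.3% |
| Weaker still | 0.06 vs 0.04 | 211 | 0.020 (-0.0215 to 0.0615) | 20% |
| One site, half of all events | 0.03 vs 0.005 | 211 | 0.025 (0.0001 to 0.0499) | 2.8% |

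At 0.06 vs 0.03 the 8.3% splits into 5.2% with the wrong sign and 3.1% exactly zero, where the ratio does not exist. The interval includes zero, so the ICER has no finite interval. In the one-site row about one event is expected in the intervention arm (211·0.005 = 1.06). Its lower limit is only a rough normal approximation.

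**Cost list against collected data.**

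| Resource | Recorded (3.4) | In the 5.2 cost list |
|---|---|---|
| Preventive dressings and application time | yes | yes |
| PU treatment materials and time | yes | yes |
| Support surface, type and days | yes, daily | no |
| Turning/positioning, type and hours | yes, daily | no; turn counts and staff minutes are not listed |

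The incremental cost is the difference between the arms' mean costs. A resource used equally in both arms cancels from it. An omitted resource shifts it by (unit price) × (difference in mean days of use). The documents give neither factor, so this gap has no computable size.

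**The case against.** The other side has several good points, and each one limits what can be claimed.

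- A reader might infer that the missing costs make the ICER unstable. They do not. They affect the numerator; the instability comes from few events in the denominator.
- A reader might infer that the incremental cost is wrong. Section 3.3 sets one standard for both arms, and equal use cancels. Bias needs differential use, which open treatment makes possible but nothing in the documents shows.
- A reader might infer that a sign change is likely under the plan. At the planning rates the chance of a difference at or below zero is 0.2%. The sign problem belongs to weaker effects, which are assumed here.
- A reader might infer that turning can be costed straight from the data. Type and hours in position are listed, but turn counts and nursing minutes are not.
- The cost sentence in 5.2 says what will be documented and does not claim to be exhaustive. The cited cost analysis may cover uncertainty or further costs. It is not part of the documents, so this cannot be checked. A general reference to a similar approach does not fix these choices in advance.
- A bootstrap and net benefit describe the uncertainty; they do not reduce it. Dropping the by-site ICERs would be a matter of preference, and the plan announces those repeats openly.

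Two things stand: the visible text states no measure of uncertainty for the ICER, and support surface is absent from its cost list without explanation.

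**Conclusion.** The point holds as a low-cost improvement in two independent parts.

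On uncertainty, the point ICER needs an interval even if the planning assumptions are right, because the denominator alone gives a 5.6-fold range. If the true effect is clearly smaller, no finite interval exists and the ratio cannot carry the conclusion. The by-site repeats rest on fewer events still. These figures assume a fixed cost difference, the risk difference as the effect, and 211 evaluable patients per arm. Real variation in costs would add to the uncertainty.

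On costs, the listed totals are incomplete for support surfaces. Whether the incremental cost is biased is open and depends on use by arm, which the trial's own daily records can show.

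Nothing here bears on the primary result.

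**What to change.** Amend the cost-effectiveness paragraph in section 5.2 as follows.

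1. State the effect as PUs avoided. Report the cost difference and the effect difference separately, each with a 95% interval from a bootstrap that resamples patients within arm and keeps each patient's cost and effect together.
2. Next to the ICER, report incremental net benefit, λ·(effect difference) − (cost difference), over a stated range of values λ per PU avoided. It involves no division, so it remains defined when the effect difference is zero or negative.
3. Do the same for the heel and sacral repeats.
4. Include support-surface days in the costs of both arms.
5. Compare positioning between arms. Cost turning only in a sensitivity analysis with a stated time assumption.

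The cost is some SAP wording, unit prices for support surfaces, a time assumption for turning and a small amount of extra analysis. No new patient data are needed.

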## 6 Methods: monitoring

### 6.1 Data monitoring

A formal data monitoring committee will not be implemented.

### 6.2 Interim analysis

One interim analysis will be done after 50% of the sample (n = 232) have completed the study. The study will be stopped when there appears to be a negligible chance of demonstrating superiority if enrolment is fully completed. After the interim analysis the study will be stopped, if the conditional power (CP) based on the observed data after 50% of recruitment is less than 60% to reject the null hypothesis, that incidences in both arms are equal (Lachin 2005).

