## 2.3 Trial design

A randomized, controlled, two arm, superiority pragmatic trial will be performed with a 1:1 allocation to the intervention and control groups. After completion of 50% of the subjects an interim analysis will be conducted to allow potential early stopping (futility stopping based on conditional power) (see 6.2).

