### 3.6 Sample size

We are planning a study of independent cases and controls with 1 control per case. Prior data of the internal quality management indicate that the average PU incidence at the ICUs of the Charité is 0.06 per month. We expect that the cumulative PU incidence for experimental subjects will be 0.01 (RR 0.17). In order to test this hypothesis we will need to study 211 experimental patients and 211 control patients to be able to reject the null hypothesis that the PU incidence in the intervention and control groups is equal with a probability (power) of 0.8. The Type I error probability associated with this test of this null hypothesis is 0.05 (two-sided). We will use the chi-squared test statistic to evaluate this null hypothesis. To prevent a possible loss of follow-up of 10%, 464 patients in total are to be included. This total sample size is comparable to a previous trial using a similar intervention and design (Santamaria et al. 2013a). The “true” PU heel and sacral PU incidence in the study might be higher, because we will include only “high” and “very high risk” patients.

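### The interim futility rule stops the trial at any conditional power below 60%, which is far from a negligible chance of success, and the 80% power in section 3.6 takes no account of it

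*Combined protocol and SAP*

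**What the plan says.** Section 2.3 announces that at the halfway point "an interim analysis will be conducted to allow potential early stopping (futility stopping based on conditional power" is foreseen. Section 6.2 sets one look, when 232 of the 464 patients have completed. It gives the purpose as stopping when "there appears to be a negligible chance of demonstrating superiority if enrolment is fully completed". It then gives a mandatory rule, under which the trial ends when "the conditional power (CP) based on the observed data after 50% of recruitment is less than 60% to reject the null hypothesis" of equal incidences. For method it cites a review of futility stopping by conditional power. The text does not state what effect is assumed for the patients still to come, and does not describe the rule as advisory. Section 6.1 adds: "A formal data monitoring committee will not be implemented".

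Section 3.6 plans 211 patients per arm to detect 6% versus 1% by chi-squared test "with a probability (power) of 0.8" at two-sided 5%, raised to 464 in total for 10% loss to follow-up. It does not mention the interim look.

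**The concern.** The aim and the rule in section 6.2 describe different designs. A conditional power of 55% means that success is more likely than not, yet the rule requires a stop. No committee is there to weigh the result, so the printed threshold is what would be applied.

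A futility rule this strict also costs power, because some trials of a truly effective dressing look only moderately promising at halfway. If section 3.6 ignores that cost, its 80% is not a property of the design as written. What is at stake is a missed effect, reported as futility. Type I error is not at risk, since stopping for futility can only reduce rejections.

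**Working it through.** **Inputs.** From section 3.6: control rate 0.06, intervention rate 0.01, two-sided alpha 0.05, chi-squared test, 211 evaluable per arm, 464 enrolled (232 per arm). From section 6.2: one look at information fraction t = 0.5, stop if CP < 0.60. CP is conditional power, Z1 and Z2 are the interim and final test statistics, and Phi is the normal distribution function.

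**Step 1: the plan's own figure.** With pooled rate 0.035,

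n = [1.960·√(2·0.035·0.965) + 0.842·√(0.06·0.94 + 0.01·0.99)]² / 0.05² = 210.9, so 211 per arm.

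Power is 80.0% at 211 and 83.6% at 232 per arm. Also 422 × 1.10 = 464. Section 3.6 is reproduced as a single-look calculation, and the only inflation is for losses. The matching drift (mean of Z2) is θ = 1.960 + 0.842 = 2.802 at 211 per arm and 1.960 + 0.979 = 2.939 at 232.

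**Step 2: the boundary on the observed trend.** CP = Phi((Z1/√0.5 − 1.960)/√0.5). CP < 0.60 is equivalent to

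Z1 < √0.5·(1.960 + 0.2533·√0.5) = 1.513, a two-sided interim p of about 0.13.

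Two cases at 116 per arm: 6 versus 2 events gives Z1 = 1.44 and CP 54%; 2 versus 0 gives Z1 = 1.42 and CP 53%. Both stop.

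**Step 3: cost when 6% versus 1% is true.** P(stop) = Phi(1.513 − θ·√0.5). Power with the rule = P(Z1 ≥ 1.513 and Z2 ≥ 1.960), correlation √0.5.

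| Observed trend | P(stop) | Power without rule | Power with rule |
|---|---|---|---|
| Normal, 211/arm | 32% | 80.0% | 63.0% |
| Normal, 232/arm | 29% | 83.6% | 67.2% |
| Binomial simulation, 211/arm | 28% | 84.9% | 68.2% |
| Binomial simulation, 232/arm | 24% | 88.3% | 72.8% |

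The simulations used 1,000,000 replicates, with looks at 105 of 211 and 116 of 232 per arm.

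Share of stopped trials that would have been significant at full enrolment: (0.8002 − 0.6297)/0.320 = 53% and (0.8363 − 0.6716)/0.286 = 58% by normal theory; 60% and 64% in the simulation.

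**Step 4: the other reading.** If CP assumes 6% versus 1% for the remaining patients, the boundary is Z1 < (1.960 + 0.2533·√0.5 − 0.5·θ)/√0.5, which is 1.044 at 211 per arm and 0.947 at 232. By normal theory P(stop) is 17% and 13%, and power 73.0% and 78.3%. In the simulation power is 78.1% and 84.3%. If CP itself is also computed from exact binomial probabilities, power is 80.6% and 85.5%.

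**Step 5: no effect.** On the observed trend the rule stops 93% of trials of an ineffective dressing. Rejection in favour of the dressing falls from 2.5% to 1.4%.

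**Step 6: higher incidence.** Section 3.6 allows that the "PU incidence in the study might be higher, because we will include only" patients at high or very high risk. Assuming relative risk stays at 0.17 (observed trend, binomial, 232 per arm), power goes from 95.4% to 84.5% at a control rate of 8%, and from 98.4% to 91.6% at 10%. Assuming 10% versus 3%, it goes from 88.4% to 74.0%.

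**The case against.** The first sentence of section 6.2 can be read as a purpose and the second as the rule. A reader can apply 60% without ambiguity, and removing one phrase would end the conflict. The threshold is a design choice, and a strict one has a benefit: it ends nearly all trials of an ineffective dressing at halfway. The cited review, which is not available here, may define the intended conditional power. The 63% is the lowest of the figures. It rests on the normal approximation with only about 15 events expected (211 × 0.06 + 211 × 0.01 = 14.8), on 211 rather than 232 per arm, and on the observed-trend reading. Under the planned-effect reading with exact calculation there is no shortfall below 80%, and higher incidence would also protect power.

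Much of this stands as a limit on size. The loss should be given as a range, and the fall below 80% does not apply to every case. It does not remove the point. Deleting the phrase would leave section 3.6 reporting a power that omits the rule. The words of section 6.2 favour the observed trend, and on that reading every method leaves power between 63% and 73% in the plan's own planning case. The 63% is also the figure on the same basis as the printed 80%.

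**Conclusion.** The concern holds and should be resolved before the interim look. A 60% cut does not match the stated aim, the effect assumed in the conditional power is not given, and the 80% in section 3.6 is the power of a design without the rule.

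With 6% versus 1% true, the rule treated as binding and conditional power on the observed trend, 24 to 32% of trials stop, and 53 to 64% of those would have reached significance. The loss is about 16 to 17 points. On the planned-effect reading, power with the rule is 73 to 86% depending on evaluable numbers and method, so the shortfall there is uncertain, but the wording conflict and the unreported cost remain. The fall below 80% applies to the planning case and to weaker effects, not to the same relative risk at a clearly higher incidence.

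**What to change.** Three changes, a few sentences in all:

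1. In section 6.2, state which effect conditional power assumes for the remaining patients.
2. Make the threshold and the stated aim agree.
3. In section 3.6, report the power with the rule in force and the method used.

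Two thresholds that would fit the stated aim, as examples (normal approximation):

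- **CP < 20% under 6% versus 1%.** Power is 79.8% at 211 per arm; 213 per arm gives a full 80%.
- **CP < 10% on the observed trend.** Power is 76.6% at 211 per arm and 80.4% at 232. It needs 230 evaluable per arm for 80%, which uses up almost all of the allowance for losses.

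The price is fewer early stops of an ineffective dressing: P(stop) under no effect falls from 93% (60%, observed trend) to 48% with the first example or 77% with the second.

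If 60% is deliberate, remove the wording about a negligible chance and restate the power. On the basis of the printed 80% that is 63% on the observed trend or 73% under the planned effect. Holding 80% with the 60% cut needs 240 evaluable per arm under the planned effect, or 316 on the observed trend. The latter is 632 evaluable, about 695 with the plan's own 10% inflation (632 × 1.10), instead of 464.

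### The 60% conditional-power trigger in section 6.2 carries no direction, so it can conflict with the superiority criterion stated just before it

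*Combined protocol and SAP*

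**What the plan says.** All references are to the combined protocol and SAP.

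- **Section 6.2, timing.** "One interim analysis will be done after 50% of the sample (n = 232) have completed the study".
- **Section 6.2, first stopping statement.** "The study will be stopped when there appears to be a negligible chance of demonstrating superiority if enrolment is fully completed". This is directional but has no number.
- **Section 6.2, second stopping statement.** The trial stops on a conditional power, computed from the interim results, of "less than 60% to reject the null hypothesis, that incidences in both arms are equal". This has a number but no direction.
- **Section 2.3** describes a "superiority pragmatic trial will be performed with a 1:1 allocation to the intervention and control groups" and calls the interim rule futility stopping. The primary objective in 2.2 is a reduction in incidence.
- **Sections 3.6 and 5.2** fix the final test: chi-squared, two-sided alpha of 0.05, null hypothesis of equal incidence.

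Section 6.2 does not say what is assumed about the effect in the second half of the trial, beyond basing the calculation on the observed data. Nor does it say which statement governs if the two disagree.

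**The concern.** Conditional power is the probability that the final analysis will produce a named event. In the numeric trigger that event is rejection of equality. A two-sided chi-squared test rejects equality whether the dressings do better or worse, so conditional power computed to the letter adds the two tails together. When the dressing arm has clearly more ulcers at half-way, the harm tail can exceed 60% while the benefit tail is close to zero. On the same data the first statement then says stop and the numeric trigger is not met.

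An analyst has to program something, and only the second statement has a threshold. At stake is whether the one interim look does what it is for, which is to end a trial that can no longer show that the dressings work.

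**Working it through.** **Inputs.** Control incidence 0.06, dressing incidence 0.01, two-sided alpha 0.05, power 0.80, 211 per arm, 464 in total (3.6). Interim at 232 (6.2). Assumed: 116 per arm at the interim and information fraction t = 232/464 = 0.5.

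**The plan's own figure.** With pooled variance and no continuity correction, mean incidence 0.035:

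n = [1.96·√(2 × 0.035 × 0.965) + 0.84·√(0.06 × 0.94 + 0.01 × 0.99)]² / 0.05² = 211 per arm.

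This reproduces the plan, and 422 × 1.10 = 464.

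**Interim statistic.** Z = (control proportion − dressing proportion) / √(p(1 − p) × 2/116), where p is the pooled proportion. Positive Z means fewer ulcers with dressings. The planning rates give about 0.06 × 116 ≈ 7 control and 0.01 × 116 ≈ 1 dressing events. The mirror image, 1 v 7, has p = 8/232 and Z = −2.16.

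**Conditional power.** Given interim Z, the final statistic is normal with mean m = Z√t + θ(1 − t) and SD √(1 − t) = 0.707.

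- Benefit tail: 1 − Φ((1.96 − m)/0.707)
- Harm tail: Φ((−1.96 − m)/0.707)
- Current-trend drift: θ = Z/√t, so m = Z/√t = 1.414·Z
- Design drift: θ = 1.96 + 0.84 = 2.80

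For 1 v 7 under the current trend, m = −3.05. The harm tail is Φ((−1.96 + 3.05)/0.707) = 0.94 and the benefit tail is below 0.0001.

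| Events, control v dressing | Z | CP to reject equality, current trend | CP for superiority, current trend | CP to reject equality, design drift |
|---|---|---|---|---|
| 7 v 1 | 2.16 | 94% | 94% | 91% |
| 1 v 4 | −1.36 | 48% | <0.01% | 1.6% |
| 1 v 5 | −1.66 | 70% | <0.01% | 0.8% |
| 1 v 7 | −2.16 | 94% | <0.01% | 0.6% |
| 2 v 8 | −1.94 | 87% | <0.01% | 0.6% |
| 7 v 14 | −1.60 | 67% | <0.01% | 0.9% |
| 7 v 16 | −1.98 | 88% | <0.01% | 0.6% |

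**Where the trigger sits.** Under the current trend, 60% in one tail requires 1.414·|Z| − 1.96 = 0.253 × 0.707, so |Z| = 1.51. The benefit-side boundary is Z = 1.51 whether or not the harm tail is counted. Counting it adds a second region, Z at or below −1.51, where the stopping threshold is not met. Under design drift the benefit-side boundary would be Z = 1.04, so the drift has to be stated in any case.

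**How often it matters.** Exact binomial probabilities of not meeting the 60% threshold, 116 per arm, current-trend drift:

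| True incidence, control v dressing | Literal trigger | Superiority-only trigger |
|---|---|---|
| 6% v 1% (design) | 76.0% | 76.0% |
| 6% v 6% | 13.6% | 6.8% |
| 6% v 9% (illustrative) | 27% | 1% |
| 6% v 12% (illustrative) | 54% | 0.1% |

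The normal approximation for no effect is Φ(−1.51) = 6.5% per side, 13.0% in total, close to the exact figure.

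**The case against.** The strongest reply is that 6.2 should be read as a whole. Both statements say the study will be stopped, and the first is as operative as the second. With 1 v 7 events the chance of showing superiority is below 0.01%, so the first statement ends the trial. Nothing in 6.2 says the trial must go on when conditional power is 60% or more. Sections 2.2 and 2.3 speak of reduction, superiority and futility, and describing power as rejection of equality is common shorthand, used in 3.6 as well, where the wrong-direction tail is negligible.

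Most of this stands. A reader might infer that the plan keeps randomising whenever the interim trend is adverse. The documents do not support that, for three reasons:

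- The superiority statement, if applied, stops the trial.
- Even the trigger read alone stops for weaker adverse trends, such as 1 v 4.
- The result needs current-trend drift, which the text suggests but does not state. Under design drift every adverse result tested stops.

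The 6% v 12% and 6% v 9% scenarios are illustrations with no basis in the plan, and percentages based on 8 to 10 events in total are approximate.

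What the reply does not remove is that the two statements can give opposite answers on the same data, and that the one with the number is the one lacking a direction.

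**Conclusion.** The point holds as an internal inconsistency in the futility rule. Taken literally with current-trend drift, the 60% trigger is not met when Z is about −1.51 or lower, although superiority is then out of reach. With no true effect this doubles the chance of continuing, from about 6.8% to 13.6%.

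The conclusion rests on 116 per arm at the interim, t = 0.5, a final critical value of 1.96, the normal approximation for conditional power, and projection of the current trend. It does not hold under design drift.

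A reader might also take this as a finding about patient safety, since 6.1 states: "A formal data monitoring committee will not be implemented". That goes too far. A futility rule is not a safety rule, and the absence of a harm boundary or a committee is a separate matter. The point is also independent of whether 60% is a sensible cut-off.

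**What to change.** In 6.2, define conditional power by direction and state the drift. For example: *conditional power is the probability, given the interim data and assuming the current trend continues, that the final test rejects the null hypothesis in favour of the dressing arm (final Z at or above +1.96, where positive Z means fewer ulcers with dressings).*

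The numeric trigger then agrees with the superiority statement, and any adverse trend gives conditional power near zero and stops the trial.

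The cost is one clause on direction and one on drift. It needs no patients and no alpha. Under current-trend drift the benefit-side boundary stays at Z = 1.51, continuation at the design rates stays at 76.0%, and power is unchanged.
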